Specific Aim #1: Determine the clinical effects of rTMS combined with CBIT in TS.

The clinical effects of active rTMS + CBIT on tics and comorbid nonmotor symptoms will be determined. Tics will be examined with the standardized Yale Global Tic Severity Scale (YGTSS) and the modified Rush Videotape Tic Rating Scale (mRVTRS), and co-morbid symptoms with the Beck Depression Inventory (BDI), Beck Anxiety Inventory (BAI), Yale-Brown Obsessive Compulsive Scale (Y-BOCS) and Adult ADHD Self-Reports Scale (ASRS). Quality of life will be assessed with the Gilles de la Tourette Syndrome – Quality of Life scale (GTS-QOL). I hypothesize that compared to baseline (T0), there will be greater reduction in tics (**Aim 1a**) and associated co-morbid symptoms and improvement of quality of life (**Aim 1b**) at T1 and T2. I also hypothesize that the accelerated protocol will be safe and well tolerated in this patient population (**Aim 1c**).

Specific Aim #2: Determine the physiological effects of rTMS combined with CBIT in TS.

The physiological effects of active rTMS + CBIT will be determined using TMS and fMRI techniques. Cortical excitability will be determined with established TMS single and paired pulse paradigms including RMT, CSP, and SICI (**Aim 2a**), and resting state fMRI will be used to monitor the blood oxygen level dependent (BOLD) activity and connectivity of the SMA (**Aim 2b**). I hypothesize that the change in TMS measures will significantly improve and BOLD activity on fMRI will decrease over SMA at T1 and T2, compared to baseline and will correlate with the clinical improvements as outlined in Specific Aim #1.

RESEARCH PLAN AND METHODOLOGY: Patients with a diagnosis of Tourette's syndrome at our movement disorders center will be enrolled. Diagnosis of TS will be established in accordance with the Diagnostic and Statistical Manual of Mental Disorders, 5th edition (DSM-5).

Inclusion Criteria: Any patient diagnosed with Tourette Syndrome > 18 years of age with moderate tic severity. Participants will be allowed to continue oral medications that they are taking for TS concurrently but will not be allowed to change their concurrent medication regimen throughout the duration of the study.

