fMRI protocol: Functional MRI will be used to record Blood Oxygen Level Dependent (BOLD) activity changes in patients at rest, using protocols similar to other studies in the literature in the TS population³⁴, as well as fMRI studies conducted by our group in other movement disorder populations.⁴⁶ The fMRI procedure should last approximately 1 hour. A 32-channel head coil will be used on a 3T MRI scanner. Subjects will wear earplugs during the sessions to minimize discomfort due to scanner noise. Anatomical images will be acquired in 170 contiguous axial slices at $1 \times 1 \times 1$ mm resolution with a T1- weighted fast spoiled gradient-recalled sequence (repetition time (TR) = 6.8 ms; echo time (TE) = 3.3 ms; flip angle = 80°). Task-based functional MRI will be acquired in 46 axial slices at $3 \times 3 \times 3$ mm resolution using a single-shot gradient echo-planar imaging pulse sequence (TR = 2500 ms; TE = 30 ms; flip angle = 80°). Each functional scan will include 176 TR volumes. Cushions will be placed in the head coil around the subject's head to minimize head-motion with strapping if needed. Repetition times (TRs), that include head motion exceeding 0.5 mm from TR to TR, will be excluded. Open source platform Analysis of Functional NeuroImages (AFNI: Version 16.0.19) will be used for the whole brain analysis. A combined 1.0-mm motion exclusion criterion in the x-, y-, and z-planes will be used. The following preprocessing steps will be followed. The first three functional MRI volumes will be removed to

account for scanner magnetization equilibrium. Following that slice-timing correction, rigid-body volume registration, co-registration of the functional MRI scan to the T1-weighted anatomical scan, non-linear spatial warping of the functional MRI scan to the MNIavg152 template will be performed. Signal-to-noise ratio will be improved by spatial smoothing using a full-width at half-maximum Gaussian kernel of 8mm.

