Location: The clinical portions of the study will be performed at the Fixel Neurological Institute; patients will have the clinical outcome measures collected in a clinic or research room.

The NeuroStar TMS machine is located in a separate TMS room within the Fixel Neurologic Institute. The MagStim Bistim machine is located in the same room.

Other devices necessary to complete the study include these portable devices which will reside in the TMS room during the study procedure:

EMG system: Bagnoli™ Desktop EMG system (Delsys, Inc., Boston, Massachusetts). It includes four surface electrodes to detect muscle movement

EEG system: ActiveTwo system (Biosemi, Amsterdam, Netherlands). It has a cap with electrodes in a preconfigured montage, using 128 Ag-AgCl electrodes.

The McKnight Brain Institute houses two 3 Tesla fMRI scanners for clinical research use, and is about a 10 minute drive from the Fixel Neurologic Institute.

Possible Discomforts and Risks: There are some possible discomforts and risks for participants taking part in this study, most of which are mild or transiently related to the study protocol and will abate afterwards.

TMS:

- Headaches – Headaches and neck aches can occur. They can be related to stabilizing the neck when measuring TMS. They are usually short lasting and respond easily to over the counter analgesics.
- Transient hearing threshold shift – There is a possibility of temporary mild hearing loss due to the noise of the TMS machine. The rate of this risk is unknown yet. Earplugs will be provided to the participant to reduce the potential for this risk.
- Seizure – A theoretical risk associated with brain stimulation. Since FDA clearance of TMS, the seizure risk is $\leq 0.1\%$ per patient (less than 1 in 1000 patients). In the event that the participant has a seizure, the study staff will immediately stop the treatment session and make sure that the participant is safe during the seizure. The participant will be watched for a period of time after the seizure to make sure he or she is feeling well. Individuals with an active seizure disorder are excluded.

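### Aim 2b predicts a fall in resting SMA activity, but the plan names only a whole-brain analysis, with no SMA region, resting index or visit contrast

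*Combined protocol and SAP*

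**What the plan says.** Under Specific Aim #2, "resting state fMRI will be used to monitor the blood oxygen level dependent (BOLD) activity and connectivity of the SMA" (Aim 2b). The directional hypothesis that follows is narrower: "BOLD activity on fMRI will decrease over SMA at T1 and T2, compared to baseline". The imaging change is also expected to correlate with the clinical improvement of Aim 1.

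The fMRI protocol section opens by saying that "Functional MRI will be used to record Blood Oxygen Level Dependent (BOLD) activity changes in patients at rest". A few sentences later it states that "Task-based functional MRI will be acquired in 46 axial slices", and no task is described anywhere. It gives sequence settings, motion limits and a preprocessing list that ends at 8 mm smoothing. On analysis it says only that AFNI "will be used for the whole brain analysis".

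Elsewhere, the Secondary Outcomes paragraph lists fMRI among several secondary measures. Regulatory Approval and Statistics describes an unpowered pilot analysed with descriptive statistics and ANOVA. The Location section says the imaging institute "houses two 3 Tesla fMRI scanners for clinical research use", while the fMRI protocol refers to a single unidentified 3T scanner.

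**The concern.** An ANOVA across visits, or a correlation with tic change, needs one number per patient per visit. The plan does not say what that number is for the SMA. The most literal reading of activity, the mean signal in the region, does not work for a resting run: BOLD intensity is in arbitrary units, and without a task there is no condition to contrast it with.

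The hypothesis also concerns one region, the one being stimulated, whereas the named analysis searches the whole brain. Such a search must use a much stricter threshold, which with 20 patients costs most of the sensitivity. At stake is the mechanistic conclusion of Aim 2: whether stimulation changed its target, and whether that change tracks clinical benefit. If region, index and contrast are chosen after the data are seen, neither a positive nor a negative result is easy to interpret.

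**Working it through.** The documents give no power, alpha, effect size or SD for fMRI, so there is no planned figure to reproduce. Three checks were made.

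**1. What is specified.**

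| Element needed | Where one would look | Found |
|---|---|---|
| Rest or task | Specific Aim #2; fMRI protocol | Rest in the aim; both rest and task in the fMRI protocol |
| SMA region | fMRI protocol | None; whole brain only |
| Activity index | Specific Aim #2; fMRI protocol | None |
| Connectivity seed and targets | Specific Aim #2; fMRI protocol | SMA named in the aim; no seed mask or targets |
| Visit contrast | Specific Aim #2; Regulatory Approval and Statistics | T1 and T2 against baseline in the hypothesis; no imaging contrast in the analysis |

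**2. Which summaries of a resting run can show a fall.** Run length is 176 × 2.5 s = 440 s. Dropping the first three volumes leaves 173 × 2.5 s = 432.5 s. Resting series of 173 volumes were simulated with a true fluctuation amplitude falling 20% (from 1.0 to 0.8, in percent of the mean), once with equal scanner gain and once with gain raised 30%.

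| Summary | Equal gain | Gain raised 30% |
|---|---|---|
| Raw mean, change | −0.1% | +29.4% |
| Mean after scaling each run to its own mean | 100 to 100 | 100 to 100 |
| SD of the scaled series | 1.00 to 0.80 | 1.00 to 0.80 |

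The raw mean follows gain. The scaled mean is constant by construction. The fluctuation amplitude recovers the true fall in both cases. The mean level therefore cannot be the endpoint, but a gain-independent resting index can.

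**3. One region against a whole-brain threshold.** Inputs: n = 20 (Enrollment). Two-sided 0.05 for one region, voxelwise two-sided 0.001 for the search, and the same standardised change in voxel and region are all assumptions.

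- Detectable paired change at 80% power and 0.05, normal approximation: (1.960 + 0.842)/√20 = 0.63 SD. With the t distribution on 19 degrees of freedom it is 0.66 SD.
- Noncentrality at 0.66 SD: 0.66 × √20 = 2.95.
- One region, critical t = 2.09: power about 80%.
- Voxelwise 0.001, critical t = 3.88: power about 23%.

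The single-region figure is for one test. If 0.05 were split equally over four tests (two measures at two contrasts), each at 0.05/4 = 0.0125, critical t is 2.76 and power about 58%, still well above 23%.

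**The case against.** The strongest reply is that the plan never equates activity with mean signal level. Fluctuation amplitude is a legitimate reading and can be computed from the planned scans. Aim 2b also names SMA connectivity, which needs no absolute level. A reader might infer from the hypothesis that the predicted decrease cannot be measured at all. The documents do not support that: the quantity is undefined, not unmeasurable. Connectivity is, however, absent from the directional hypothesis and has no targets, so naming it does not close the gap.

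Second, a whole-brain analysis does not exclude an SMA test, and the aim already identifies the region. That is fair, but no such test is written down, and the sensitivity cost applies to the analysis that is. The preprocessing list may also be incomplete, since the section points to protocols in cited studies. Its silence on scaling is therefore not a decision against it.

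Third, if a task is in fact used, a condition contrast could exist and the argument about resting level would not apply. This stands, and it is why rest versus task must be settled first. As written, no task, timing or contrast is given.

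Fourth, a reader might infer from the two scanners on site that visit differences will be scanner artefact. The Location section describes facilities. No passage says that both scanners are used or that anyone changes between them, and if nobody switches there is no effect. This is a risk the plan leaves uncontrolled, not a shown flaw.

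Finally, fMRI is one of several secondary outcomes in a small pilot. That limits the weight of the point but does not remove it.

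**Conclusion.** The concern holds as a mismatch between hypothesis and analysis. Aim 2b predicts a change in one region, and the plan names only a whole-brain analysis, with no region, resting index or imaging contrast. The mean level of a resting run cannot fill the gap.

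The illustrative size is about 80% power for a single SMA test against about 23% at a voxelwise threshold of 0.001, for a paired change of 0.66 SD in 20 patients. This rests on the assumed alphas, on all 20 patients having usable scans at both visits, and on the same standardised change in voxel and region. None of these is stated in the documents. No size can be put on scanner or session artefact from the documents, and none is claimed. The conclusion also depends on the runs being resting, which the fMRI protocol leaves contradictory.

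**What to change.** 1. Reconcile the resting and task-based descriptions in the fMRI protocol section. If there is a task, describe it and its contrast; the steps below are for resting runs.
2. Make the Aim 2b test a prespecified anatomical SMA region of interest from an atlas. The rTMS protocol section places the coil by scalp measurement (4 cm anterior to the vertex) and describes no registration to MRI, so a mask centred on the stimulated site is not available from the plan as written.
3. Name one gain-independent resting index, for example fractional amplitude of low-frequency fluctuations, with a predicted fall. Add SMA-seed connectivity with the striatum and thalamus, the network the Background already cites. The particular index is a matter of choice; naming it beforehand is the point.
4. State the T0-T1 and T0-T2 contrasts, which one leads, and how the remaining tests are treated. Use the same index for the correlation with tic change.
5. Keep the whole-brain map as exploratory, with its threshold stated.
6. As a precaution only, keep each participant on one scanner, or record which was used at each visit.

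The cost is a few sentences in Specific Aim #2, the fMRI protocol and the statistics paragraph, plus at most a small scheduling constraint. No extra scans or patients are needed.

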There is emerging data from case reports, open-label studies, and small randomized controlled trials to that low-frequency rTMS targeted to the SMA can lead to tic reduction.²⁷⁻³⁴ However, these studies are small, many involved only a single stimulation session, and the follow-up period was limited. Furthermore, these studies did not investigate whether rTMS in conjunction with CBIT could lead to synergistic benefits. rTMS is postulated to enhance motor and cognitive learning through the Hebbian mechanisms of neuroplasticity.³⁵⁻³⁷ Thus, when rTMS is used in conjunction with behavioral and cognitive therapies, it may potentiate the synapses that are recruited to complete the intended tasks.^{35,37} Therefore, the **primary goal** of this proposal will be to determine whether low-frequency rTMS delivered to the SMA has synergism with CBIT therapy in patients with TS. The central hypothesis of the proposal is that rTMS will potentiate the effects of CBIT, resulting in improved outcomes in patients with TS. In addition, given the known benefits of rTMS on depression and obsessive-compulsive disorder (OCD)^{38,39}, it is hypothesized that rTMS plus CBIT may not only lead to tic improvement, but also result in improvement in comorbid depression and OCD symptoms observed in patients with TS.

Since CBIT and rTMS both typically require multiple sessions over several weeks to be effective, these could present barriers to patient compliance. Delivering CBIT therapy via a virtual platform is just as effective via telehealth as it is in-person.^{40,41} Accelerated rTMS protocols which condense the number of sessions into a consecutive day paradigm have been successfully and safely employed in other patient populations.⁴²⁻⁴⁵ Therefore, a consecutive 4-day accelerated rTMS protocol followed by the recommended protocol for CBIT of 8 sessions in 10 weeks using a virtual platform will be implemented to mitigate these logistical challenges.

This will be an open-label study for which all subjects will receive active rTMS. Following active rTMS, all participants will undergo 10 weeks of tele-CBIT and whether rTMS will augment the effects of CBIT will be determined (**Aim 1**). The effects at baseline (T0), after rTMS (T1), and after CBIT therapy (T2) will be measured (Figure 1). In addition to the clinical outcomes, the physiological changes underlying the clinical effects will be investigated (**Aim 2**).

OBJECTIVES/SPECIFIC AIMS:

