Exclusion Criteria: 1) Presence of metallic objects or neurostimulators in the brain, 2) pregnancy, 3) history of active seizures or epilepsy, 4) contraindications to receiving fMRI, such as claustrophobia 5) inability to participate in CBIT due to other underlying cognitive or medical condition

[figure not shown]

Figure 1. Study design and timeline. TS patients with moderate severity symptoms will undergo active rTMS followed by 10 weeks of tele-CBIT. Clinical, physiology measures, and imaging will be collected at three time points (baseline/T0, T1, T2).

Enrollment: Our target is to enroll 20 total patients in the study. In order to enroll 20, we will need to screen more than that number. We anticipate that we will need to screen 64 patients in order to find 24 that are eligible for enrollment. Of those 24, we anticipate that 4 will choose not to participate in the study.

IRB approved informed consent will be obtained. The study procedures will be explained, and subjects will have a detailed medical history and neurological examination. Patients will have primary and secondary outcome measures performed at four time

points: Baseline (T0), following rTMS (T1), and following CBIT (T2) (Figure 1). The study protocol will take place over approximately 11-12 weeks. Details of specific parts of the protocol are included below.

Primary Outcome: Tic severity will be measured with YGTSS and mRVTRS. Videos of participants will be recorded at T0, T1, and T2, which will be scored by two independent blinded raters.

Secondary Outcomes: BDI, BAI, Y-BOCS, ASRS, and GTS-QOL; TMS, EEG, and fMRI outcomes.

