CBIT protocol: All CBIT sessions will be conducted by an occupational therapist ([name], OTD, OTR/L) who is a certified therapist in CBIT. Patients will have the option of having the first introductory CBIT sessions scheduled in-person since they will already be at the center for rTMS and outcome measures. For convenience, all other CBIT sessions will occur through a secure telemedicine platform. Each CBIT session will last approximately 1 hour. Following CBIT protocol, there will be 8-10 tele-CBIT sessions over 10 weeks, at the therapist's discretion. Each session will be individualized to each patient's needs depending on tic type and severity.

EEG protocol: High-Density EEG using 128 electrodes as the setup will be implemented. Each EEG session should last about 1 hour. Patients will be seated comfortably in a chair and a cap will be stretched across the scalp. This cap has 128 contacts where the electrodes will be connected using biosoluble glue. The electrodes will be placed appropriately by a clinician or technician trained to place the EEG electrodes. The patient's electrical activity will be recorded under two conditions: at rest and asking the patients to voluntarily suppress their tics (Figure 3B and D).

Safety: Since the most important safety concern with rTMS is the possibility of seizure, participants with active seizure disorder or those at increased risk of seizure will be excluded. Low frequency protocols carry less risk of seizure as compared to high frequency protocols given that high frequency generates cortical excitability.⁴⁷ In spite of the theoretically increased risk of seizure in accelerated rTMS protocols, several accelerated high-frequency protocols have been safely performed in other patient populations and have been tolerated well by patients without evidence of increased adverse events.⁴²⁻⁴⁵ A similar protocol to the one proposed in this study, using the same TMS system that I will be using, has been safely completed in the pediatric Tourette's population.³⁴ Patients will be screened prior to admission into the study, and those at risk for adverse reactions will be excluded. Those selected for participation will be monitored closely for adverse events. Other mild side effects that participants may experience secondary to TMS include transient eye pain, toothache, muscle twitch, facial pain, neck stiffness, and pain or discomfort at the application site and skin.

Clinical Assessments:

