Possible Benefits: The participant may or may not benefit from taking part in the study. All participants will undergo CBIT, which has previously been studied and is one of the first-line treatments for TS given its favorable efficacy^{11,48-49}, so participants may benefit from participation in CBIT. Half the subjects will receive active rTMS which may augment the CBIT sessions, leading to even further reductions in tic severity and frequency. The information gathered from this study will benefit the neurology department and the larger research community as we continue to seek the most efficacious treatments for Tourette's Syndrome.

Regulatory Approval and Statistics: The study will be approved by the University of Florida Institutional Review Board, and all subjects will provide written informed consent. The study is highly feasible given the relatively large number of patients with Tourette's that are seen at UF. This is a pilot study so it has not been powered for statistical significance. We will use descriptive statistics and ANOVA to run analysis on the data that has been collected.

Confidentiality: Information collected about the patient will be stored in locked filing cabinets or in computers with security passwords. Only certain people have the legal right to review these research records, and they will protect the secrecy (confidentiality) of these records as much as the law allows. These people include the researchers for this study, certain University of Florida officials, the hospital or clinic (if any) involved in this research, and the Institutional Review Board (IRB; an IRB is a group of people who are responsible for looking after the rights and welfare of people taking part in research). Otherwise the research records will not be released without participant permission unless required by law or a court order.

Researchers will take appropriate steps to protect any information they collect about participants. However, there is a slight risk that information about participants could be revealed inappropriately or accidentally. Depending on the nature of the information such a release could upset or embarrass them, or possibly even affect their insurability or employability.

If the results of this research are published or presented at scientific meetings, patient identity will not be disclosed.

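### Medication is frozen only once the study starts: with no stable period required before T0 and no comparison arm, the effect of a recent drug change can be counted as an effect of rTMS + CBIT, mainly at T2.

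*Combined protocol and SAP*

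**What the plan says.** **Entry.** Inclusion Criteria admits "Any patient diagnosed with Tourette Syndrome > 18 years of age with moderate tic severity". Oral drugs for TS may continue, and participants "will not be allowed to change their concurrent medication regimen throughout the duration of the study". No length of stable treatment before T0 is given.

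**Exclusions.** Of the five listed, the only one that concerns CBIT is "inability to participate in CBIT due to other underlying cognitive or medical condition". Other sections add exclusions. Safety says "Patients will be screened prior to admission into the study, and those at risk for adverse reactions will be excluded", and Possible Discomforts and Risks adds implants, nursing, gadolinium allergy and severe kidney disease. None concerns a recent drug change, outside or earlier CBIT, or earlier rTMS.

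**Design and contrast.** The Background states "This will be an open-label study for which all subjects will receive active rTMS". Specific Aim #1 expects that "compared to baseline (T0), there will be greater reduction in tics" at T1 and T2. Under Primary Outcome, "Tic severity will be measured with YGTSS and mRVTRS".

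**Analysis.** Regulatory Approval and Statistics names descriptive statistics and ANOVA, mentions no covariate for earlier treatment, and says that this pilot is not powered.

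**The concern.** The freeze shows that the sponsor wants drug effects kept out of the measured change. It does so only if the regimen has reached a steady effect by T0. As written, a patient whose tic or psychiatric drug was changed the week before T0 is eligible and must then stay on the new regimen while its effect develops. With no concurrent control, that development cannot be separated from rTMS + CBIT. Blinded video rating does not help, because the tics themselves would have changed. The secondary outcomes include depression, anxiety, OCD and ADHD scales, so recent psychotropic changes matter beyond tics.

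There is a related gap for non-drug treatment. The freeze covers medication only, so CBIT or similar therapy taken outside the study is not ruled out. Earlier CBIT and earlier rTMS do not bar entry, and nothing ties them to the analysis. Earlier CBIT is foreseeable: the plan says that CBIT "is one of the first-line treatments for TS given its favorable efficacy", and it recruits at the sponsor's own movement disorders center. The Background also says that benefits of multi-session rTMS outlast the stimulation.

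**Working it through.** **1. Is there a rule elsewhere?** The inclusion, exclusion, safety, risk and statistics sections were read for a stability window, a washout or a CBIT-naive rule. There is none. The nearest item is the detailed medical history taken at enrolment, to which no entry rule or analysis is attached.

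**2. Which contrast is exposed?** Patients attend for 5 consecutive days at the start, 4 of them with rTMS, so T0 and T1 are about 5 days apart. The window of 14 days either side of each event could stretch this. T2 follows 10 weeks of CBIT, about 11-12 weeks in. A drug effect that develops over weeks therefore appears mainly in T2 minus T0.

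**3. Shift in the mean.** The documents give no rates and no drift, so both are assumed. If *k* of 20 patients drift by *D* YGTSS points in the same direction, the shift is *k*/20 × *D*:

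| *k* | *D* = 3 | *D* = 5 | *D* = 8 |
|---|---|---|---|
| 2 | 0.3 | 0.5 | 0.8 |
| 4 | 0.6 | 1.0 | 1.6 |
| 6 | 0.9 | 1.5 | 2.4 |

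Opposite drifts cancel. With *k* = 6 and *D* = 5, if 4 patients improve and 2 worsen, the shift is (4 − 2)/20 × 5 = 0.5 rather than 1.5.

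**4. Effect on a test.** The plan states no alpha, SD or effect size, so there is no figure to reproduce. As an illustration, take a two-sided one-sample t-test on the change with n = 20, an assumed alpha of 0.05 and no true study effect. A fraction *f* drifts by *d* SDs of the change score, all in one direction. The mean bias is *f* × *d*, the SD is √(1 + *f*(1 − *f*)*d*²), and the noncentrality is bias/SD × √20. For *f* = 0.25 and *d* = 1, that is 0.25/√1.1875 × 4.472 = 1.03, giving a rejection rate of 16.4%.

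| *f* | *d* = 0.25 | *d* = 0.5 | *d* = 1.0 |
|---|---|---|---|
| 10% | 5.1% | 5.5% | 6.9% |
| 25% | 5.8% | 8.1% | 16.4% |
| 50% | 8.2% | 17.8% | 47.6% |

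The assumed 2 to 6 of 20 is 10% to 30%, so the first two rows are the closest. The 50% row means 10 of 20 patients.

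**The case against.** The strongest reply is that this is a small, unpowered, single-arm pilot. Even with perfectly stable treatment before T0, natural fluctuation, regression to the mean and expectation would remain mixed with the effect of rTMS + CBIT. That is true, and the missing comparator is the larger problem. But lack of power excuses imprecision. It does not excuse a bias that one eligibility line would reduce.

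The reply also limits how far the point can be taken. A reader might infer four stronger things that the documents do not support:

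- **That T1 is equally affected.** By the visit plan it falls days after T0, so little drift is expected.
- **That prior CBIT biases T2 minus T1 downward.** It can act either way: continuing gain, or less room for further gain. The room argument is weak in any case, since every entrant must still have moderate tics.
- **That the cohort differs from the CBIT patients behind the under-40% tic reduction in the Background.** The documents do not describe those patients' earlier treatment, and no comparison with them is planned.
- **That patients with prior CBIT should be excluded.** That is a choice of target population, and recruitment has no slack: 64 screened, 24 eligible, 24 − 4 = 20 enrolled. If 4 of 20 had prior CBIT (assumed), excluding them would mean 64/0.8 = 80 screened.

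**Conclusion.** The gap stands. The plan controls medication from entry onward but not before T0, and it has no rule on CBIT outside the study. In a single-arm study judged against T0, a recent drug change can therefore be counted as an effect of rTMS + CBIT, chiefly at T2. Whether it will be, and in which net direction, cannot be known from the documents.

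Under the assumed same-direction drift of 3 to 8 YGTSS points in 2 to 6 of 20 patients, the shift runs from 0.3 to 2.4 points. These are upper limits for each assumed pair, because drifts in opposite directions reduce them. The documents give no SD or meaningful-change threshold to judge them against, and the calculation does not cover mRVTRS. The effect is negligible if few patients had a recent change and material if many did. Earlier CBIT and rTMS are a matter of recording and description, with no presumed direction of bias.

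**What to change.** 1. Add to eligibility that the tic and psychotropic regimen be unchanged for a period before T0, with the length set by the sponsor. Patients with a recent change may enter later.
2. Extend the in-study freeze to CBIT or other tic-directed psychotherapy outside the study.
3. Record prior CBIT and prior rTMS at screening, and report the T0, T1 and T2 changes descriptively by that history. Do not exclude these patients.

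**Cost.** The information can come from the medical history already planned. Some patients will enter later or be lost. If the assumed 2 to 6 of 20 with a recent change were all lost, screening would rise from 64 to about 64/0.9 = 71 or 64/0.7 = 91. Later entry reduces that. The groups by treatment history will be small and can support description only.
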